#### 3.9.4.1 CCI (Exploratory Objectives CCI)

CCI  
CCI  
CCI  
CCI  
CCI  
CCI  
CCI

### **3.9.5 Risk of Random Error**

The precision of the RTI episode rates depends on a range of parameters, including the number of patients included in the study, the average follow-up time available for the patients, and the rate of loss to follow-up. The risk of random error increases and the precision of the rates decreases (i.e., the CIs become wider) with fewer included users of OM-85 and comparator patients, less follow-up time per patient, and/or higher rate of patients lost to follow-up. The risk of random error will be discussed with reporting the results of the study, considering the number of patients included in the analysis and the available follow-up time. However, the data source feasibility assessment showed that the average follow-up time in the selected data sources would allow the analysis at the selected time points with no significant loss to follow-up, which would limit the risk of random error.

At the same time, the strategy to include patients to this study using the TTE framework is not identical to the feasibility study. Specially, the feasibility study did not apply the TTE framework where all patients meeting the inclusion criteria are followed during the initiation grace period, to define in which treatment strategy patients are categorised to. The feasibility study included all patients ever prescribed OM-85 meeting preliminary inclusion and exclusion criteria. In the TTE framework applied here, only patients who initiate OM-85 within 30 days of meeting inclusion criteria (i.e. CED) are included. Additionally, when patients with multiple candidate CEDs will be included to the study population by choosing one CED randomly, there is risk that some OM-85 users will be included to the study as non-users (based on that CED; another CED not selected could be the one leading to OM-85 use). Therefore, fewer OM-85 exposed patients will be included in this full study using the TTE framework. Even though using the TTE framework is a compromise to study size, it minimises bias and improves the internal validity of the study.

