**Table 2 Events Ending Follow-up and Censoring Variables**

		Operational Definition
Events ending follow-up, throughout the follow-up		
1	End of 24-month follow-up	2 years from end of initiation grace period for each patient
2	Death	For THIN Italy and Belgium: last contact date, which defines exit from the database regardless of reason (death, physician change, or choosing to exit the database) For Inspur China: Date of death directly available by a report from social security sent to Inspur
3	Loss to follow-up/exit of data source	For THIN Italy and Belgium: last contact date, which defines exit from the database regardless of reason (death, physician change, or choosing to exit the database) For Inspur China: Date of lost to follow-up, which defines exit from the database regardless of reason (death or migration to another city)
Censoring during follow-up, after the 30-day initiation grace period: deviation from the assigned treatment strategy		
1.1	OM-85 group: None	-
1.2	SOC/non-user group: at first date of OM-85 prescription during follow-up (after the initiation grace period)	Same
1.3	Sensitivity analysis: The SOC/non-user group are censored at the first date of prescription for any bacterial lysate (including OM-85), the OM-85 group would be censored at the first date of prescription of any bacterial lysate other than OM-85 during follow-up	Same

Note: CED: cohort entry date; SOC: standard of care; THIN: The Health Improvement Network.

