**Table 4 Inclusion Criteria**

	Inclusion Criteria	Operational Definition
1	Patient aged $\geq 1$ year of age at CED	Aged $\geq 1$ year at CED
2	Patient has $\geq 1$ RTI episodes during the 12-month baseline period prior to CED	$\geq 1$ RTI episodes within a 12-month period during the inclusion period. The CED is the date of the 2 nd , 3 rd , ... or n th RTI episode (i.e., date of fulfilling the inclusion criteria). If one patient has multiple CED during the inclusion period, the CED will be selected randomly. The definition of an RTI episode provided in Section 3.3.2.1
3	Patient has $\geq 12$ months of continuous enrolment in the database prior to CED	$\geq 12$ months of continuous enrolment in the database prior to the CED. Operationally, patients were required to have entered the database at least 12 months before the CED to be included in the study. In THIN (Belgium and Italy), this can be defined by a district variable for entry to the database: first contact date. In Inspur (China), patients are required to have records in the database at least 12 months before the CED (during the 12-month baseline period) to be eligible for inclusion
4	No record of a prescription of any bacterial lysates in the 12-month baseline period prior to CED	No record of the country-specific drug codes ( Appendix 4 ) during the 12-month baseline period

Note: CED: cohort entry date; RTI: respiratory tract infection; THIN: The Health Improvement Network.

Inclusion criterion 2 on the requirement of having  $\geq 1$  prior RTI episodes is important to apply because OM-85 is indicated for prevention of recurrent RTIs (24). However, patients in the SOC/non-user comparator group may still have fewer prior recurrent RTIs than the OM-85 group receiving preventive therapy. Therefore, prior recurrent RTIs will also be used in the PS matching of the compared exposure groups. The impact (preventive effect) of OM-85 on the recurrence of RTIs is anticipated to be higher in patients with an increased recurrence risk (35). Hence, the analyses will also be stratified by the number of RTI episodes prior to CED (see [Table 5](#)).

The inclusion of patients is not defined by sex. Sex is instead defined at CED and considered in the PS.

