Exploratory objective [redacted]	CCI [redacted] CCI [redacted]	CCI [redacted] CCI [redacted] CCI [redacted] CCI [redacted] CCI [redacted] CCI [redacted] CCI [redacted]	CCI [redacted] CCI [redacted] CCI [redacted] CCI [redacted] CCI [redacted]
Exploratory [redacted]	CCI [redacted] CCI [redacted]	CCI [redacted] CCI [redacted] CCI [redacted] CCI [redacted] CCI [redacted] CCI [redacted]	CCI [redacted] CCI [redacted] CCI [redacted] CCI [redacted]
Exploratory objective [redacted]	CCI [redacted] CCI [redacted] CCI [redacted]	CCI [redacted] CCI [redacted] CCI [redacted] CCI [redacted] CCI [redacted]	CCI [redacted] CCI [redacted] CCI [redacted] CCI [redacted] CCI [redacted]
Exploratory objective [redacted]	CCI [redacted] CCI [redacted] CCI [redacted]	CCI [redacted] CCI [redacted] CCI [redacted] CCI [redacted] CCI [redacted]	CCI [redacted] CCI [redacted] CCI [redacted] CCI [redacted] CCI [redacted]

Objective	Outcome	Definition	Measurement
Exploratory objective CCI	CCI CCI CCI	CCI CCI CCI CCI	CCI CCI CCI CCI CCI CCI CCI
Exploratory objective CCI	CCI CCI CCI	CCI CCI CCI CCI	CCI CCI CCI CCI CCI CCI CCI

CCI

 THIN databases (Italy and Belgium) do not cover hospitalisation stays or visits to the ICU or emergency care, while the Inspur database (China) does not cover primary care.

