### **3.4.2 Inspur: China**

Inspur is a government-owned company and is authorised to manage city-level data in the Tianjin city of China, which is a large northern city. The database includes Electronic Medical Record (EMR) data, at the patient level, from 82 public hospitals in Tianjin, including secondary and tertiary hospitals in Tianjin city. Secondary hospitals in China are mid-sized regional facilities with 100 to 500 beds, serving district or county levels, while tertiary hospitals are larger, comprehensive medical centres with over 500 beds, offering more specialised services, advanced technology, and typically serving city, provincial, or national populations. Compared to other

databases in China which cover only tertiary hospitals, Inspur collects regional data from secondary and tertiary hospitals, which increases the representativeness of the Chinese population. The database links EMR data, laboratory data and image data, however, the data are not linkable to other sources outside of the Inspur network. It is noteworthy that only one ethics committee (EC)/IRB is needed for the Inspur database rather than needing each hospital's approval, which facilitates the EC/IRB process. Although the time frame covered in Inspur starts from 2005, reliable data electronic collection/coverage spans from January 2018 to latest available data, which were therefore used for the study period time frame. The feasibility assessment found that most of the variables required for the study are captured with good completeness in the Inspur database, with the exceptions of vaccine administration and lung function tests. These data will therefore not be collected and analysed from Inspur as part of this study. Furthermore, the feasibility counts of patients treated with OM-85 revealed that the majority are children under 11 years of age; however, the adult population remains significant in size (utilising preliminary inclusion and exclusion criteria).

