### **3.7.3 Analysis of Primary Endpoint: RTI Rates (Primary Objectives 1-2, Secondary Objectives 3-4, Exploratory Objectives CCI)**

The primary outcome is the rate of RTIs episodes measured during different periods of interest, as specified in the objectives. The rate of RTI episodes will be estimated by calculating the total number of RTI episodes observed, divided by the total number of person-time (e.g., person-years) during a period of interest. Rates of RTI episodes will be estimated separately in patients initiating preventive treatment with OM-85 and in the SOC/non-user group. Furthermore, rates of RTI episodes during the baseline period will serve as reference in each treatment group to evaluate the effects of therapy during follow-up.

Comparative analysis comparing the RTI rates before and after OM-85 initiation, and analysis comparing RTI rates in the two exposure groups will be performed using approaches as described in the General Considerations. Generalised linear models with a Poisson distribution or negative binomial distribution (to account for over-dispersion) will be used to estimate the association between the initiation of OM-85 and the outcome of RTI rates, with the natural logarithm of the time at risk as offset (42).

The analyses will be identical for the exploratory objectives **CCI** **CCI** (Section 3.2.2.3).

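### In China only death or migration counts as loss to follow-up, so time spent outside the Inspur hospitals counts as RTI-free and can push the before-after rate ratio below 1

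*Protocol*

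**What the plan says.** **The assurance.** Section 3.9.5 credits the feasibility assessment with showing that "the average follow-up time in the selected data sources would allow the analysis at the selected time points with no significant loss to follow-up". It gives no loss rate. Section 3.4.1 states average follow-up for THIN Belgium (9 years) and THIN Italy (7 years). Section 3.4.2 gives no such figure for Inspur.

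**When follow-up ends for loss (Table 2).**
- THIN: "last contact date, which defines exit from the database regardless of reason (death, physician change, or choosing to exit the database").
- Inspur: "Date of lost to follow-up, which defines exit from the database regardless of reason (death or migration to another city").

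**What Inspur can see.** Section 3.4.2 describes records "from 82 public hospitals in Tianjin, including secondary and tertiary hospitals in Tianjin city" and adds that "the data are not linkable to other sources outside of the Inspur network". A footnote to Table 8 states that "the Inspur database (China) does not cover primary care".

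**How the rate is formed.** Section 3.7.3 estimates it by "calculating the total number of RTI episodes observed, divided by the total number of person-time (e.g., person-years) during a period of interest".

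**What is required before cohort entry (Table 4).** For Inspur, "patients are required to have records in the database at least 12 months before the CED". At least one RTI episode must fall in the 12 months before the cohort entry date (CED), and the CED is itself the date of an RTI episode. Nothing comparable is required after the CED.

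**What is said about missed infections.** Section 3.9.2.2 accepts that RTIs may go unrecorded because the sources do not cover all care settings. It expects this to act towards the null.

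**The concern.** Inspur is a hospital record system, and most RTIs do not need a hospital. A patient who stays in Tianjin but takes later infections to a community clinic, or to a hospital outside the network, is not lost under Table 2. That patient's time stays in the denominator while the numerator cannot grow.

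The before and after periods are treated differently. Entry depends on recent use of the network, and follow-up does not. If use of the network falls off after the CED, the after rate in primary objective 1 drops with no help from the drug. That would favour OM-85, the opposite of the direction expected in Section 3.9.2.2.

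Section 3.9.5 handles loss only as a matter of precision. Unobserved time is a bias, and more patients do not reduce it.

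**Working it through.** **1. The plan's own precision figure.** Section 3.5 gives an F-based interval for the rate ratio. With 2 episodes per person-year at baseline and equal person-time, a = 2 × IRR × PY and b = 2 × PY. At IRR 0.9 and 350 person-years, a = 630 and b = 700. The interval is 0.807 to 1.004, width 0.197, as in Table 9. All 32 cells of Table 9 reproduce. The arithmetic is sound, but it takes every counted person-year as able to yield a recorded RTI.

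**2. Model for unobserved time.** Let u be the fraction of counted person-time in which no RTI can be recorded. For an inert drug:

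- before-after ratio = (1 − u_after) / (1 − u_before)
- between-arm ratio = (1 − u_OM-85) / (1 − u_SOC)

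**3. Assumption on leaving.** The protocol gives no leaving share, so q is assumed: a share q of patients stops using the network, evenly over 24 months.

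- At 24 months each leaver is unobserved for half the window on average: u = q × 0.5.
- At 12 months half of the leavers have gone, each unobserved for half of that window on average: u = (q/2) × 0.5.

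**4. Primary objective 1, baseline taken as fully observed (u_before = 0).**

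| q | u at 12 months | False ratio, 12 months | u at 24 months | False ratio, 24 months |
|---|---|---|---|---|
| 10% | 0.025 | 0.975 | 0.05 | 0.95 |
| 20% | 0.05 | 0.95 | 0.10 | 0.90 |
| 30% | 0.075 | 0.925 | 0.15 | 0.85 |

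These values are at the upper end for each q, because some baseline time is unobserved too. At q = 20% and 24 months, u_before = 0.05 gives 0.90/0.95 = 0.947, and u_before = 0.10 gives 0.90/0.90 = 1.00.

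**5. Primary objective 2.**
- Equal leaving in both arms: ratio 1.00, no bias.
- 10% of OM-85 and 20% of SOC patients leave: 0.975/0.95 = 1.03 at 12 months and 0.95/0.90 = 1.06 at 24 months.
- The reverse: 0.95/0.975 = 0.97 and 0.90/0.95 = 0.95.

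**6. Size of the study does not help.** Put a false ratio of 0.90 into the Section 3.5 formula with equal person-time. At 350 person-years per period the interval is 0.807 to 1.004. At 5,000 it is 0.875 to 0.926, which is narrower and excludes the true value of 1.

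**7. Would ending follow-up at the last record test this?** In the model of step 3, suppose the last record falls at the time of leaving and those who stay have records to the end of the window. Episodes and counted time then fall together: 0.95/0.95 = 1.00 at 12 months and 0.90/0.90 = 1.00 at 24 months. The analysis therefore responds to the bias.

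**The case against.** Part of this is already disclosed. Section 3.9.2.2 names missed RTIs and the hospital-only setting in China. Section 3.9.1.1 warns that detection falls when access to care falls, and asks for caution with the before-after results. Secondary objective 7 reports healthcare visits in both arms at each time point. Section 3.9.5 is about random error, so treating loss there as a precision matter is partly a question of placement. All of this stands. None of it connects missed care to the person-time that Table 2 keeps counting, and none of the sensitivity analyses listed in Section 3.7.7 (episode length, other bacterial lysates, clone-censor weighting) tests it.

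Three stronger readings are tempting, and the protocol does not support them:

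- **That the assurance is true in China only by definition.** The feasibility report is not shown, and nothing says it used the Table 2 rule. What can be said is that the assurance does not establish that time in China is observed.
- **That the before year is fully observed.** Table 4 requires records and at least one RTI, not complete capture. Baseline infections treated in primary care are unseen as well, and only the difference in capture moves the ratio.
- **That the average follow-up times imply a sizeable loss.** The averages concern THIN, where exits are censored at last contact. They are also shortened by the end of data in July 2024, so they give no exit rate. They say nothing about unobserved time in China.

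**Conclusion.** The point holds in a limited form. For China, the protocol counts time after a patient has stopped using the network, and it requires network contact before cohort entry but not after. This can push the before-after ratio below 1 for an inert drug. The expectation in Section 3.9.2.2 of bias towards the null is therefore not assured for primary objective 1.

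The size cannot be derived from the protocol. If 20% leave evenly over 24 months and baseline is fully observed, the false ratio is 0.95 at 12 months and 0.90 at 24 months. The latter equals the effect that Section 3.5 calls small and bases its minimum study size on. With less leaving, or with similar gaps before and after, the bias shrinks or vanishes. In primary objective 2 it can go either way and cancels only if both arms leave equally.

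Belgium and Italy are not affected by this mechanism in the same way, because follow-up there ends at last contact. The change should be made, but it does not call the main design into question.

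**What to change.** 1. **Section 3.9.5:** for Inspur, limit the assurance to death and migration.
2. **Section 3.9.2.2:** name unobserved person-time in China as a possible bias that may favour OM-85 in primary objective 1, and qualify the statement on direction.
3. **Section 3.7.7:** for China, repeat both primary objectives with follow-up ended at the patient's last Inspur record of any kind, searched up to the end of data. This is the analogue of the THIN last-contact rule already in Table 2.
4. **Reporting:** for China, give by arm the time from last record to end of follow-up.

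A looser rule that allows 12 months after the last record would not do the job. The OM-85 prescription is itself a record, so the 12-month result of primary objective 1 could not change. At 24 months with q = 20%, counted time would fall only to 0.975, and the false ratio would move only from 0.90 to 0.90/0.975 = 0.92.

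**Cost.** One added analysis, run by Inspur on data it already holds, plus wording. The last-record rule depends on healthcare use and removes some time that was truly free of infection. It should be read beside the main analysis and should not replace it.

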## **4 PROTECTION OF HUMAN SUBJECTS**

### **4.1 Ethical Considerations**

The procedures set out in this study protocol are designed to ensure that the Sponsor and CRO abide by the principles of the International Society for Pharmacoepidemiology GPP guidelines (49). The study will also be carried out in compliance with local legal requirements. No ethical approvals are needed for accessing data from Belgium and Italy, unless the results from the THIN databases are intended for publication. For accessing data in China, an ethical approval will be submitted to the ethical committee of the Tianjin main centre in China (Section 3.4).

### **4.2 Informed Consent**

This study utilises exclusively secondary data from data sources collected as part of routine care. Hence, no patient data will be collected for the purpose of this study. For Belgium and Italy, no consent is required as data are anonymised. Patients are informed of the data collection and can choose to exit the database, the non-opposition principle is applied. For China, no consent is

required, as only aggregated data will be disclosed from Inspur to Parexel and the Sponsor. Therefore, informed consent from the participants is not applicable.

### **4.3 Protocol Approval and Amendment**

Before the start of the study, the study protocol and any other relevant documents will be approved by the ethical committee of the Tianjin main centre in China in accordance with local legal requirements. For Belgium and Italy, no protocol approval process is required for the conduct of this study using the THIN databases, as detailed in this protocol. However, in case the results from the THIN databases are intended for publication, a protocol approval of the THIN Euroboard is required. This approval will be obtained before the conduct of the study. The Sponsor must ensure that all ethical and legal requirements have been met before extracting patient data for the study.

To alter the protocol, amendments must be written, with approval from the appropriate personnel, and approval from the ethical committee of the Tianjin main centre in China in accordance with local legal requirements.

Administrative changes may be made without the need for a formal amendment. All amendments will be distributed to all protocol recipients, with appropriate instructions.

### **4.4 Confidentiality**

All study findings and documents will be regarded as confidential. The CRO (Parexel) must not disclose such information without prior written approval from the Sponsor.

The confidentiality of the patients included in the study is ensured by the data holders in the following way. For the THIN databases, all individual-level patient data delivered to the Parexel study team are anonymised, thus preventing re-identification of any individuals in the data. For Inspur, all analysis is carried out by the data holder and only aggregated results are shared with the Parexel study team.

## **5 MANAGEMENT AND REPORTING OF ADVERSE EVENTS/ADVERSE DRUG REACTIONS**

This study utilises exclusively secondary data from data sources collected as part of routine care. Hence, no patient data will be collected for the purpose of this study. Therefore, management and reporting of adverse events and adverse reactions as part of this study is not applicable.

## **6 PLANS FOR DISSEMINATING AND COMMUNICATING STUDY RESULTS**

The study will be registered in the EMA-HMA catalogue upon finalisation of the protocol and prior to data access. By signing the study protocol, the Sponsor agrees with the use of results of

the study for the purposes of national and international registration, publication, and information for medical and pharmaceutical professionals.

The results obtained within the study are the exclusive property of the Sponsor. The Sponsor recognises the ethical obligation to disseminate findings of potential scientific or public health importance (e.g., results pertaining to the safety of a marketed drug). The study results may be included in abstracts sent to scientific congresses and/or articles sent to scientific reviews. Specific plans for disseminating and communicating the study results will be produced when the results are available.

## **8 APPENDICES**

### **8.1 Appendix 1: List of Stand-alone Documents**

The following stand-alone documents are available on request.

NA

